Surgical resection for tumor analysis before the commencement of SGT-53/Temozolomide treatment is an optional procedure. For these patients, SGT-53 will be administered twice during the week prior to surgical resection of the tumor. 14-21 days post-surgical resection, patients will receive SGT-53 and Temozolomide in 28 day cycles. These patients who respond to treatment (at least stable disease by RANO) may receive three additional cycle of SGT-53/Temozolomide therapy at investigator's discretion. The primary objective of this surgical resection is to assess nanoparticle tumor delivery by analysis of the presence of exogenous wt p53 in the tumor.

All patients enrolled in the study will be evaluated for PFS, PFS-6 and OS.

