4.6.3.1 Primary Endpoints

PFS-6 using the RANO criteria (see Section 18.2) will be used as primary endpoints.

4.6.3.2.Secondary Endpoints

- Safety of the combination of SGT-53 and Temozolomide.
- PFS, OS
- Anti-tumor activity of the combination of SGT-53 and Temozolomide based upon the RANO criteria.
- The induction of apoptosis by SGT-53 in the tumor (optional procedure).
- Nanoparticle delivery (optional procedure)

4.6.4. Statistical hypothesis and sample size:

A total of 26 patients will be enrolled. A maximum of 6 patients will be enrolled to participate in the optional surgical resection for tumor analysis.

Patients who have received at least one dose of study drug will be considered evaluable for safety and toxicity endpoints. Patients who require a dose interruption or reduction during the initial cycle will remain evaluable for toxicities if the reduction or interruption is due to a DLT. Patients who do not complete one cycle of treatment but do not have a DLT may be replaced as described in more detail in Section 9.6.

The primary endpoint for the trial is PFS6. Progression-free survival will be defined as the time from study enrollment until the time of first occurrence of disease progression, relapse, or death due to disease.

The analysis of the biological correlate data in patients with surgical resection for tumor analysis has the overall goal of providing an increased understanding of the ability of SGT-53 to cross the Blood-brain Barrier and be delivered into tumor cells in the brain. As such, the objective of the tumor analysis is qualitative rather than quantitative. It should be noted that in the Phase I dose escalation trial of SGT-53, the presence of the exogenous wtp53 delivered by SGT-53 was found to be present in the tumors in a DNA dose dependent manner. Moreover, even the lowest dose of SGT-53 (0.6mg DNA/infusion) was not only found to be present in the tumors of the patients, but to have some anti-tumor effect. A DNA dose 6-fold higher (3.6mg DNA/infusion) is being used in this trial.

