9.3.2. SGT-53 Infusion Reactions

Infusion reactions are defined as any adverse event that occurs during the infusion of SGT-53 or during the two hours following completion of the infusion. Hypersensitivity reactions are those events defined by NCI criteria, e.g., bronchospasm, dyspnea, etc.

If infusion reactions occur during the infusion of SGT-53, the infusion will be discontinued and appropriate medical care administered. SGT-53 is to be administered only by physicians or nurses with training and experience with the administration of chemotherapeutic agents. All medications and interventions used to treat infusion reactions will be recorded and reviewed by the DSMB at the routine scheduled meetings (see Section 14).

The SGT-53 infusion may resume at a slower infusion rate if the symptoms resolve within two hours. If the infusion recurs at the same grade or higher, the infusion will be terminated and no further infusions of SGT-53 administered to that patient.

If a hypotensive reaction (BP < 90 systolic) occurs during infusion of SGT-53, infusion should be discontinued and not resumed during that visit. SGT-53 infusions may resume if the symptoms of hypotension have resolved by the time of the next scheduled infusion. Should this occur during SGT-53 infusions and not resolve within 24 hours the patient will not receive any further treatments (neither Temozolomide nor SGT-53) that week. The treatments will begin again the following Monday, repeating the interrupted week.

Should a second acute hypotensive reaction (BP < 90 systolic) occur during infusion of SGT-53 the patient will be removed from protocol and be replaced.

In the event that an infusion reaction consists of respiratory wheeze, including symptomatic bronchospasm or any grade 3 or 4 hypersensitivity reaction, the infusion is to be permanently discontinued and the patient replaced.

If infusion reactions occur, acetaminophen, diphenhydramine, steroids or other medications may be given for symptom control as needed. Although prolonged use of systemic corticosteroids to prevent allergic reactions is discouraged, intermittent use of corticosteroids is permitted. Use of corticosteroids (dose, name, start/off dates) should also be documented in CRFs

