9.3.4. Outpatient Clinic for Subsequent SGT-53 Infusions

For subsequent infusions, subjects will be infused with SGT-53 in the outpatient infusion unit of in one of the outpatient ambulatory treatment centers at the clinical trial sites. The treatment centers are staffed with medical personnel and equipment to treat emergency and non-emergency events and is highly experienced with phase I and II trials. Subjects

will be monitored for two hours, as in Section 9.3.1., and will be discharged only if medically stable. The subject can be monitored for up to 8 hours in the clinic prior to discharged if medically stable. If necessary, the subject can be admitted for 23 hour observation as described for the first infusion (Section 9.3.3.).

9.4. Study drug discontinuation and study withdrawal:

Every reasonable effort should be made to maintain patient compliance and participation in the study. However, all patients are free to withdraw from participation in this study at any time, for any reason, and without prejudice.

A patient will be considered as withdrawn from the study if, and only if, he/she withdraws consent, or is lost to follow-up after unsuccessful attempts by the investigator to contact the patient.

The Investigator may terminate a patient from the study for administrative reasons, or in the investigator's opinion, to protect the patient's best interest. Reasons may include the following:

- Patient withdraws consent and refuses to continue procedures/observations.
- If at any time, continued participation in the study is determined not to be in the best interest of the patient.
- Development of a severe (grade 4) or intolerable adverse event that does not resolve within a 14 day time-frame.
- Development of a significant intercurrent illness.
- Deterioration in patient's disease status such that chemotherapy is no longer indicated.
- Termination of the study by the Sponsor. Patient's care will not be affected in the event of premature termination of this study.
- At any time during study in patients with Progressive Disease as defined below, as determined by Investigator (see Section 18.2.)

If a patient is withdrawn before completing the study, the reason for withdrawal will be entered on the appropriate CRF. Whenever possible and reasonable, the evaluations that were to be conducted at the completion of the study and radiographic tumor measurement should be performed at the time of premature discontinuation.

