For grade 2 events of increased bilirubin, AST, ALT, dyspnea, or DIC, the dose of SGT-53 can be held for up to two weeks. If the grade 2 event resolves within two weeks, then infusion of SGT-53 can resume at the same dose per calendar at incident week + 1-2 weeks (i.e., treatment would be made up and moved 1-2 weeks later).

For non-hematological events other than increased bilirubin, AST, ALT, dyspnea, or DIC, participants who develop a > or = to grade 2 toxicity (except for alopecia, or fever, chills, hypotension that respond to treatment) or grade 3 fatigue will discontinue twice-

weekly infusions until the toxicity level reduces to at least grade 1. Infusions will be held for one week intervals, and infusions that are withheld will be made-up (i.e. moved 1-2 weeks later). If the toxicity does not resolve within two weeks, study drug will be discontinued.

In the event that a patient is removed from the study for reasons other than toxicity, they can be replaced at the same dose level.

Patients who go off-treatment after receiving any infusions of SGT-53 will be considered eligible for evaluation of toxicity. Patients withdrawing consent prior to initiation of therapy will be replaced at the same dose level.

9.4.1. Patient follow up after study discontinuation:

All patients who received treatment with SGT-53 must be followed-up for 30 days after discontinuation of study drug. The 30-day follow-up visit should include a physical examination, vital signs, concomitant medications and assessment of AEs/SAEs and Urine analysis. Blood samples will be taken for: Hematology (CBC with differential, platelet count), Chemistries (BUN, Cr, Na⁺, K⁺, CO₂, Cl, Mg⁺⁺, Ca⁺⁺, phosphorus, albumin, alkaline phosphatase, ALT, AST, total bilirubin, total protein, glucose, LDH), PT/PTT, and D-dimer. Patients who permanently discontinue study drug(s) for reasons other than complete response, progression, or death should also have visits approximately every 2 months for the first year that should include a MRI, physical examination, vital signs, and recording of concomitant medications for glioblastoma.

Patients who are withdrawn from study treatment due to a complete response will have the 30-day follow-up visit as described above. Further follow-up visits every 2 months will include only a physical/neurological exam, concomitant medications, vital signs and a MRI.

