9.5. Replacement policy

Patient replacement will be decided by the Safety Monitoring Committee.

9.6. **Dose Modification**

Reduction/interruption of dosing for adverse events may take place at any time. Below are guidelines for dose modification for drug-related toxicities as well as guidelines for their management. These parameters are only a guide and are not intended to supersede the clinical judgment of the treating physician. All adjustments should be made in consultation with the Medical Monitor and the Sponsor.

All dose modifications should be based on the worst preceding toxicity. If study treatment is being held due to toxicity, scheduled visits and all assessments should continue to occur except the dosing of the study drug.

9.7. **Dose Modification Plans:**

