			after the first event, if recurs
			reduce to 100 mg/m ² etc
			If recurs at lowest dose of TMZ
			(100 mg/m ² or less), withdraw
			from study. If at any time it does
			not resolve within 14 days,
Tr1 1	ZUNA	<75 000 to	withdraw from study.
Thrombo-	<lln td="" to<=""><75,000 to	Grade 3: <50,000 to 25,000/mm³	</lln>	<75,000 to	Grade 3: <50,000 to 25,000/mm ³
cytopenia	$75,000/\text{mm}^3$	50,000/mm ³	Grade 4: <25,000/mm ³
	Proceed at	Proceed at	If resolves to grade ≤ 2 within 14 days, rechallenge at same dose of
	current dose	current dose	SGT-53, and reduce dose of TMZ
	current dosc	current dosc	in increments after each event
			according to Table 9.7.2b below,
			i.e.in Cycle 1 reduce to 100
			mg/m^2 after the first event, in
			Cycle 2 reduce to 150 mg/m ² after
			the first event, if recurs reduce to
			100 mg/m ² etc
			If recurs at lowest dose of TMZ
			(100 mg/m ² or less), withdraw
			` '
			not resolve within 14 days,
			withdraw from study.
			(100 mg/m ² or less), withdraw from study. If at any time it does not resolve within 14 days,

Table 9.7.2.b Dose de-escalation for TMZ:

Treatment Cycle	Agent	Schedule	Level	Level	Level
			0 (Target Dose)	-1	-2
Cycle 1	TMZ	Days 9-13	150 mg/m^2	100mg/m^2	
Cycle 2 onwards		Days 9-13	200 mg/m ²	150 mg/m ²	100 mg/m^2

In the event of grade III or higher toxicity associated with TMZ after cycle 1, treatment will be interrupted and patient monitored for resolution of toxicity, with subsequent reinitiation of treatment. TMZ dosing will resume after complete resolution of toxicities to Grade II or less.

The dose of Temozolomide will only be escalated to 200 mg/m2 if the patient meets the following criteria: If the CTC nonhematologic toxicity for Cycle 1 is \leq Grade 2 (except for alopecia, nausea, and vomiting, diarrhea, or fever, chills or hypotension which respond promptly to treatment and lasts less than 24 hours), absolute neutrophil count (ANC) is \geq 1,500/mm³, and the platelet count is \geq 100,000/mm³. The dose remains at 200 mg/m2 per day for the first 5 days of each subsequent cycle except if toxicity occurs. If the dose was not escalated at Cycle 2, escalation should not be done in subsequent cycles.

If more than a 2 week delay is required to meet hematologic parameters for treatment, the patient must be removed from study and replaced.

9.7.3. Dose de-escalation for SGT-53:

Permitted dose modifications for SGT-53

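### Sections 9.3.2 and 9.7.2 order replacement of already-treated patients, and nothing says who then counts in the Simon rule's first 18 and 26

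*Combined protocol and SAP*

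**What the plan says.** **Ordered replacement.** Three toxicity triggers apply to patients who are already on study drug:

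- Section 9.7.2, last paragraph: "If more than a 2 week delay is required to meet hematologic parameters for treatment, the patient must be removed from study and replaced".
- Section 9.3.2: should a second reaction with systolic pressure below 90 "occur during infusion of SGT-53 the patient will be removed from protocol and be replaced".
- Section 9.3.2 again: after wheeze, including symptomatic bronchospasm, or "any grade 3 or 4 hypersensitivity reaction, the infusion is to be permanently discontinued and the patient replaced".

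**Permitted replacement.** Section 4.6.4 says that patients who do not finish one cycle but "do not have a DLT may be replaced as described in more detail in Section 9.6". Section 9.6 is about dose modification and holds no replacement rule. Section 9.4 adds that if a patient is "removed from the study for reasons other than toxicity, they can be replaced at the same dose level". Section 9.5 is one sentence: "Patient replacement will be decided by the Safety Monitoring Committee".

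**Who is evaluated.** Section 4.5.1 states: "All patients enrolled in the study will be evaluated for PFS, PFS-6 and OS". Section 9.4 states: "A patient will be considered as withdrawn from the study if, and only if, he/she withdraws consent, or is lost to follow-up". Section 9.4.1 schedules MRI about every 2 months in the first year for patients who stop drug for reasons other than complete response, progression or death. The analysis set in section 8.2 is for secondary endpoints only.

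**The decision rule.** Section 4.6.4 fixes it at the first 18 patients and then 26, with a 10% type I error limit at PFS6 15% and 70% power at 30%. It says that patients with and without resection both enter the calculation. It does not mention replaced patients.

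**The concern.** A Simon design takes its error rates from a fixed number of patients and fixed cut-offs. Once a treated patient is exchanged because of something that happened on treatment, the plan must say whose 6-month status enters the count. Two of the possible answers change the operating characteristics. Counting both the replaced patient and the replacement tests more than 18 and 26 patients against cut-offs set for 18 and 26. Dropping the replaced patient selects the counted group by a post-treatment event, which biases PFS6 if that event is related to outcome. With no rule in place, the choice could also be made after outcomes are known. At stake is the single go/no-go decision of the trial, in a design with little slack: 0.083 attained against a limit of 0.10.

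**Working it through.** **Inputs.** From section 4.6.4: stage 1 has 18 patients and continues with 3 or more progression-free; the final count is 26 and is positive with 7 or more; null rate 0.15, alternative 0.30. The documents give no rate for the replacement triggers, so the share replaced, *f*, and the PFS6 of replaced patients, *q*, are assumptions.

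**1. The plan's own figures.** With true rate *p*,

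P(go) = Σ over x ≥ 3 of P(Bin(18, p) = x) × P(Bin(8, p) ≥ 7 − x).

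At p = 0.15:

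| x in stage 1 | P(x) | P(enough in stage 2) | product |
|---|---|---|---|
| 3 | 0.2406 | 0.0214 | 0.0051 |
| 4 | 0.1592 | 0.1052 | 0.0168 |
| 5 | 0.0787 | 0.3428 | 0.0270 |
| 6 | 0.0301 | 0.7275 | 0.0219 |
| 7 or more | 0.0118 | 1 | 0.0118 |

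The sum is 0.0826. At p = 0.30 the same formula gives 0.7007. The stated design is reproduced, and a search confirms 26 as the smallest total meeting both limits.

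**2. Both patients counted, cut-offs 3 and 7 unchanged.** With *k* extra patients, all at p = 0.15, the range covers how many of the extras fall in stage 1:

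| k | type I error |
|---|---|
| 0 | 0.083 |
| 1 | 0.097–0.098 |
| 2 | 0.113–0.115 |
| 3 | 0.129–0.133 |

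This needs no assumption that replaced patients do worse than others.

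**3. Replaced patients dropped, replacement counted.** If PFS6 over all treated patients is 0.15, the rate among those counted is (0.15 − q·f)/(1 − f). For example, f = 0.10 and q = 0 gives 0.15/0.90 = 0.1667. Entering these rates in the formula of step 1:

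| PFS6 of replaced patients (q) | type I error, f = 5% | type I error, f = 10% |
|---|---|---|
| 0 | 0.103 | 0.128 |
| 7.5% | 0.092 | 0.104 |
| 15% | 0.083 | 0.083 |
| 22.5% | 0.074 | 0.064 |

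Per 26 counted, the number replaced is 26f/(1 − f): 1.4 at 5% and 2.9 at 10%.

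**4. All treated patients counted in order of enrolment.** If everyone's 6-month status is known, step 1 applies: 0.083 and 0.701. If a share *f*, unrelated to outcome, has no 6-month assessment and counts as failure, the rate becomes p(1 − f):

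| f | type I error | power |
|---|---|---|
| 5% | 0.066 | 0.640 |
| 10% | 0.052 | 0.575 |

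**The case against.** The strongest reply is that the plan already leans the right way. Section 4.5.1 evaluates all enrolled patients for PFS-6, section 9.4 narrows withdrawal to lost consent or loss to follow-up, section 9.4.1 keeps MRI going after drug is stopped, and the first 18 is most naturally read as enrolment order. This stands as evidence against dropping replaced patients. It does not settle the count: if all are evaluated and replacements are added, more than 26 patients meet a cut-off built for 26, as in step 2.

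The size can also be disputed. One extra patient, or 5% dropped with PFS6 of 7.5%, stays within the 10% limit. The nearest figures on frequency do not measure the triggers. In section 4.4.1, 8 of 11 phase 1 patients had grade 1–2 hypotension, but the trigger is a second fall below 90 systolic during infusion. In section 7.1, fewer than 10% of anaplastic astrocytoma patients needed hospitalization, transfusion or discontinuation for myelosuppression, and criterion 7 of section 6.1 requires prior temozolomide tolerance. All of this stands, and it is why the shares above are labelled as assumed.

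A reader might go further and infer two things. One is that PFS6 will be biased upward. Nothing in the documents says that patients removed for cytopenia or infusion reactions have worse PFS6, and if they do better, type I error falls. The other is that the replacement orders contradict section 9.5. Specific triggers and a general committee decision can coexist, with the committee deciding the cases that are not spelled out.

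**Conclusion.** The concern holds as a gap in the counting rule. The plan orders replacement of treated patients for toxicity, permits it in other cases, and does not say how they fit the fixed 18 and 26. Under the reading that section 4.5.1 favours, with replacements added and cut-offs kept, two extra patients are enough to pass the 10% limit (about 0.11), and three give about 0.13. If replaced patients are dropped instead, type I error lies between 0.064 and 0.128 for 5–10% replaced and PFS6 of 0–22.5% among them, with no change at 15%. Those shares and outcomes are assumptions. The documents support the statement that the error rates are undefined once a treated patient is replaced and can exceed the limit. They do not support a claim of certain upward bias or of a conflict with section 9.5. The design figures themselves are correct. This should be changed before the stage 1 count is taken.

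**What to change.** 1. In sections 9.3.2, 9.7.2, 9.4 and 4.6.4, allow replacement only for patients who never received study drug.
2. Where a patient is taken off for toxicity, change the wording about removal from the study or protocol, or withdrawal from the study, to *discontinued from study treatment*. This applies to sections 9.3.2, 9.7.1 and 9.7.2, and Tables 9.7.2a and 9.7.3. State that the 2-monthly MRI visits of section 9.4.1 apply to these patients.
3. Add to section 4.6.4: *PFS6 is judged in the first 18 and the 26 treated patients in order of enrolment, whether or not treatment stopped early; a treated patient without a 6-month progression-free assessment counts as not progression-free.*
4. Correct the cross-reference in section 4.6.4 from 9.6 to 9.5.

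**Cost.** Amendment wording only; the MRI visits are already planned. The price is in power: 0.701 is kept only if 6-month status is obtained for every treated patient, and step 4 shows the loss if it is not. The same convention lowers type I error, so it errs on the cautious side. Complete follow-up after stopping drug is what protects the design.

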	If occurs at this second reduced dose of SGT-53 withdraw from study.

10. STUDY ASSESSMENTS:

10.1. Pretreatment Evaluation

Pre-study assessments will be performed according to the Study Calendar (Section 18.1.) before study registration and include:

Within 7 days of registration:

- Radiographic tumor measurements
- Complete medical history
- Concomitant medication assessment
- Baseline Review of Systems and AE documentation
- Physical examination (all body systems)
- Vital signs (temperature, blood pressure, pulse rate, and respiratory rate)
- KPS Performance Status

- 12-lead electrocardiogram
- Limited Echocardiogram with the results reviewed by a cardiologist
- Serum chemistry including: sodium, chloride, carbon dioxide, potassium, calcium, phosphorous, magnesium, BUN, creatinine, blood sugar (random), albumin, alkaline phosphatase, alanine aminotransferase, aspartate aminotransferase, bilirubin (total, direct), and total protein.
- Coagulation parameters
- CBC with differential and platelet counts
- Urinalysis

Within 3 days of initiation of treatment:

• Pregnancy test (for nonsterile women of childbirth potential)

10.1.1. Laboratory Certification and Normal Values

Before initiation of the study, the laboratory certification for all local laboratories to be used in the study must be provided to the Sponsor. Normal ranges of all laboratory parameters required during the study must be provided by the Investigator.

10.2. Evaluation During Study

The starting dose of SGT-53 will be 3.6 mg of DNA. If necessary, dose de-escalation for SGT-53 will proceed according to the dose de-escalation scheme in Table 9.7.3 above. Assessment of DLTs will be made based on the first cycle (4 weeks of treatment). At the end of the first cycle, if no DLT are observed, additional patients may be enrolled and treated simultaneously. If the first patient experiences a DLT in the first cycle (4 weeks), then only one additional patient will be enrolled and evaluated for DLT. If the second patient does not experience DLT in the first cycle (4 weeks), then additional patients may be enrolled simultaneously.

10.2.1. Patients with Optional Surgical Resection for Tumor Analysis:

Beginning 5 days prior to scheduled surgical resection of their recurrent glioblastoma, patients will initiate 3.6mg DNA dosing/infusion with SGT. Dosing will continue through the day before surgery.

• One portion of the surgical section will be saline rinsed and flash frozen for measurement of exogenous wt p53 in tumor tissue, one portion will be immediately formalin-fixed for evaluation of PD biomarkers of activity of SGT-53 including but not limited to Annexin V and TUNEL staining. In addition, one portion of fresh tissue will be used for flow cytometry and/or immunohistochemistry analysis to determine the level of apoptosis in Cancer Stem Cells (CSC) and bulk tumor cells. Any remaining tumor tissue from an earlier procedure will be collected and stored in a research tissue bank at Georgetown University or the clinical site.

Following surgery, an MRI scan should be done no later than 72 hours from the time of surgery.

Following recovery from surgical resection (POD ~14-21), patients will restart SGT-53 and TMZ on the morning of Cycle 1 Day 1 (C1D1). Each cycle will consist of 28 days. Patients will return to the clinic for twice weekly (every 3rd or 4th day) infusions of SGT-53 for three weeks (see treatment schedule diagram in section 9.1.1). Temozolomide will be taken daily by mouth daily on days 9-13 of each cycle. During week 4 of each cycle the patient will not receive any treatments. Patients will return to the clinic on Day 29 (C2D1) and Day 57 (C3D1) for evaluation. If the drug has been well tolerated, continued dosing will be permitted even if they appear to be progressing.

Patients will be monitored for response and disease progression with MRI brain scans every 2 cycles (8 weeks) and/or at the end of cycle 3, or earlier if progressive disease is suspected.

All patients who participate in this study will continue treatment with SGT-53 and TMZ after surgery. The following conditions should be satisfied before initiation of treatment with SGT:

- 1) They have recovered from the effects of surgery including adequate wound healing.
- 2) A brain MRI should be done no later than 72 hours in the immediate post-operative period to best assess the extent of residual measurable disease post-operatively.
- 3) The patient has followed the study requirements for birth control and pregnancy testing since the initial pre-operative doses of SGT and TMZ.
- 4) Post-operatively, patients must have adequate bone marrow function (absolute neutrophil count > 1,500/ μ L and platelet count of >100,000/ μ L), normal coagulation profile (PT/PTT), adequate liver function (SGPT, SGOT, and alkaline phosphatase <2.5 times upper limit of normal and bilirubin < 1.5 X upper limit of normal), adequate renal function (BUN or creatinine <1.5 times upper limit of institutional normal within 7 days prior to starting therapy.
- 5) The patient continues to meet all the eligibility criteria of the study outlined above.

10.2.2. Patients Not undergoing Surgical Resection:

Patients who have had surgery for recurrent glioblastoma will follow the guidelines listed above for patients with optional surgical resection for tumor analysis.

If no surgery has been performed, patients will start SGT-53 and TMZ on the morning of Cycle 1 Day 1 (C1D1). Each cycle will consist of 28 days. Patients will return to the clinic for twice weekly (every 3rd or 4th day) infusions of SGT-53 for three weeks (see treatment schedule diagram in section 9.1.1). Temozolomide will be taken daily by mouth daily on days 9-13 of each cycle. During week 4 of each cycle the patient will not

receive any treatments. Patients will return to the clinic on Day 29 (C2D1) and Day 57 (C3D1) for evaluation. If the drug has been well tolerated continued dosing will be permitted even if they appear to be progressing.

Patients will be monitored for response and disease progression with MRI brain scans every 2 cycles (8 weeks) and/or at the end of cycle 3 or earlier if progressive disease is suspected.

10.2.3. All Patients:

Evaluations done at each clinic visit are detailed in Section 18.1.

Patients will return to clinic at least weekly for assessments (until the last week of protocol therapy). Refer to the Study Calendar, Appendix 18, for evaluations to be completed during each clinic visit. Each clinic visit will include: assessment of vital signs (blood pressure, pulse and temperature). The following will be performed only on a weekly basis (usually on the first visit of each week) unless clinically significant values were obtained at the previous visit: physical exam; assessment of the ECOG/ Karnofsky Performance Status; assessment of concomitant medications; assessment of adverse events; completion of a serum chemistry panel; completion of a CBC with differential. At the beginning of every cycle a urinalysis panel will be completed. A 12-lead ECG and echocardiogram will be performed at baseline. Additional ECGs/ echocardiograms should be obtained on any patient who demonstrates signs or symptoms of myocardial degeneration. Additionally a 12-lead ECG will be performed 2 hours and 24 hours after the first infusion of SGT-53. A 12-lead ECG will be performed weekly (2 hours postinfusion) during the first 2 weeks of cycle 1, and at the End Of Treatment (EOT) visit. If these patients receive additional rounds of SGT-53/Temozolomide a 12-lead ECG will only be performed as necessary and at the EOT visit.

The first two subjects enrolled in this trial under the current protocol will be monitored for PT/PTT, D-dimer and LDH at baseline/screening; in cycle 1 ~20 hours after the first infusion (during the 23 observation period), and weekly during cycle 1, and once in two weeks during cycles 2 and 3 and at the exit visit. If these patients receive additional rounds of SGT-53/Temozolomide PT/PTT, D-dimer and LDH will be monitored once in two weeks during cycle 1 and monthly in cycle 2 and beyond.

Subsequent subjects will be monitored for PT/PTT, D-dimer and LDH at:

- (i) baseline/screening;
- (ii) in cycle 1 (a) ~20 hours after the first infusion (during the 23 observation period)
- (iii) at the exit visit.

Patients who are responding to treatment (at least stable disease by RANO) may receive three additional cycle of SGT-53/temozolomide therapy at investigator's discretion. Alternatively, they may continue on Temozolomide alone at investigator's discretion.

10.2.4. End of Treatment Evaluations (Day 85, at the end of Cycle 6 if the patient received cycles 4-6, or for premature withdrawal/study drug discontinuation)

Once a patient has completed study treatment, including premature withdrawal/study drug discontinuation, the patient should complete an End of Treatment Visit. During this visit the following assessments will be completed:

- Radiographic tumor measurement
- Complete medical history
- Physical examination (all body systems)
- Karnofsky Performance Status
- Vital signs (temperature, blood pressure, pulse rate, and respiratory rate)
- Concomitant medication assessment
- Serum chemistry including: sodium, chloride, carbon dioxide, potassium, calcium, phosphorous, magnesium, BUN, creatinine, blood sugar (random), albumin, alkaline phosphatase, alanine aminotransferase, aspartate aminotransferase, bilirubin (total, direct), and total protein.
- CBC with differential and platelet counts
- 12-lead electrocardiogram
- Limited Echocardiogram, only if needed
- Urinalysis
- Assessment of adverse events

10.3. **Follow-up**

If the patient was removed from the Study for toxicity, the patient should be followed with weekly clinic visit and laboratory studies as appropriate, at clinical trial site or the patient's local MD, until the AE has resolved to baseline or is documented as irreversible.

All patients who received treatment with SGT-53 must be followed-up for 30 days after discontinuation of study drug. The 30-day follow-up visit should include a physical examination, vital signs, concomitant medications and assessment of AEs/SAEs and Urine analysis. Blood samples will be taken for: Hematology (CBC with differential, platelet count), Chemistries (BUN, Cr, Na⁺, K⁺, CO₂, Cl, Mg⁺⁺, Ca⁺⁺, phosphorus, albumin, alkaline phosphatase, ALT, AST, total bilirubin, total protein, glucose), PT/PTT, D-dimer, LDH.

Patients who permanently discontinue study drug(s) for reasons other than complete response, progression, or death should also have visits approximately every 2 months for the first year that should include a MRI, physical examination, vital signs, and recording of concomitant medications for glioblastoma.

Patients who are withdrawn from study treatment due to a complete response will have the 30-day follow-up visit as described above and in Sections 5 and 9.4.1. Further follow-up visits every 2 months will include only a physical/neurological exam, concomitant medications, vital signs and an MRI.

